13. STATISTICAL CONSIDERATIONS

13.1 Study Design/Endpoints

This is a phase I trial of the combination of dabrafenib, trametinib, and INCB039110 in patients with BRAF-mutant advanced solid tumors. The primary objective of the study is to determine the maximum tolerated dose (MTD) of the combination; secondary objectives will provide preliminary estimates of efficacy and toxicity. The escalation and stopping rules imply that the incidence rate for DLT will be less than 33% at the MTD. Following the identification of the MTD, up to an additional 20 patients will be enrolled in a dose expansion cohort at the MTD.

Toxicities and lab values will be graded according to the NCI Common Toxicity Criteria for Adverse Events (v4.0). Dose-limiting toxicities will be scored and will be defined as in Section 5.2.

Dose escalation will use a standard “3+3” approach, beginning in dose level 1, with dosing and rules for escalation and de-escalation described in the tables below. Tolerability assessments will be based on cycle 1 alone. The MTD is defined as the highest dose level at which 0 or 1 of six patients has experienced a DLT. If an excessive number of toxicities occur at the initial dose level 1, the dose will be reduced to the fall-back dose of -1. If dose level -1 has excessive toxicity, the study will stop.

Number of Patients with DLT at a Given Dose Level	Dose Escalation Rule
0 out of 3	Proceed to the next dose level and enroll 3 patients
1 out of 3	Enroll and treat 3 additional patients at this dose level
≥ 2 out of 3	Dose escalation will be stopped. The MTD will be one dose below this dose level. Three (3) additional patients will be entered at the next lower dose level if only 3 patients were treated previously at that dose.
1 out of 6	Proceed to the next dose level.
≥ 2 out of 6	Dose escalation will be stopped. The MTD will be one dose below this dose level. Three (3) additional patients will be entered at the next lower dose level if only 3 patients were treated previously at that dose.
If $\geq 2/3$ or $\geq 2/6$ patients at dose level 1 experience dose limiting toxicities, dose level -1 will be enrolled. If dose level -1 proves too toxic, the study will stop.	Dose escalation will be stopped. The MTD will be one dose below this dose level. Three (3) additional patients will be entered at the next lower dose level if only 3 patients were treated previously at that dose.

The following table shows the probability of escalating the dose for various true, but unknown, rates of unacceptable toxicity.

True DLT Rate	Probability of Dose Escalation
0.10	0.91
0.20	0.71
0.30	0.49
0.40	0.31
0.50	0.17
0.60	0.08

A patient will be replaced if determination of DLT cannot be adequately assessed because of rapid disease progression or if treatment is stopped during the first cycle of therapy for reasons other than toxicity.

When the MTD had been determined, up to 20 patients will be enrolled in an expansion cohort of patients with melanoma to obtain preliminary toxicity and efficacy estimates. Patients treated at the MTD during the dose escalation phase may be included in the expansion cohort. Toxicity and efficacy rates will be summarized with 90% exact binomial confidence intervals.

The table below summarizes the probabilities of observing at least one patient with a severe or unexpected toxicity in the expansion cohort for a range of incidence rates.

True Incidence of Unexpected or Severe Toxicity	Probability of Observing One or More Patients with Toxicity among 20
0.01	0.18
0.03	0.46

True Incidence of Unexpected or Severe Toxicity	Probability of Observing One or More Patients with Toxicity among 20
0.05	0.64
0.08	0.81
0.09	0.85
0.10	0.88
0.15	0.96

Secondary endpoints that will be assessed for the 20 patients treated at the MTD in the dose-expansion cohort are: objective response rate, progression-free survival (PFS), 6-month PFS, and 1-year overall survival (OS).

Objective response rate is defined as the proportion of patients with complete or partial response as their best response to therapy. At the time of each restaging, patients will be classified as achieving complete response (CR), partial response (PR), stable disease (SD), progressive disease (PD), or non-evaluable for response according to RECIST (Version 1.1) criteria. Objective response will be determined by the best overall response designation recorded between the date of first dose of trial therapy and the date of objectively documented disease progression or cessation of trial therapy, whichever occurs first. For patients without documented progression or cessation of trial therapy, all available response designations will contribute to the objective response determination.

The distributions of progression-free survival (PFS) and overall survival (OS) will each be summarized using the product-limit method of Kaplan-Meier. Median times for each endpoint will be presented with two-sided, 90% confidence intervals estimated using log(-log(survival)) methodology. Kaplan-Meier estimates of 6-month PFS and 1-year OS will also be presented with two-sided, 90% confidence intervals.

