1.2 Study Design

The primary objective of the dose escalation component of the study is to define the maximum tolerated dose (MTD) of the triple combination of dabrafenib, trametinib, and INCB039110. The table below summarizes the planned dose levels. Dose escalation will follow a standard 3+3 design beginning in dose level 1. The doses of dabrafenib and trametinib for Dose Level 1 were selected based upon the results of the phase I study showing excellent tolerability and safety, and that this combination appears to be associated with a reduced incidence and severity of *some* of the toxic effects of monotherapy with either a BRAF or MEK inhibitor, as well as excellent clinical activity. ([name] *et al.* 2012).

Dose Level	Dabrafenib [BID/PO]	Trametinib [QD/PO]	INCB039110 (mg QD)
-2	75 mg	1 mg	100 mg
-1	150 mg	2 mg	100 mg
1	150 mg	2 mg	200 mg
2	150 mg	2 mg	300 mg
3	150 mg	2 mg	400 mg

It is conceivable that additional cohorts may be necessary to pick an optimal treatment regimen with the three agents. As such, if toxicity is seen at a dose level where dose modification is necessary and the prior, lower dose level was treated without DLT, then additional dose cohorts between the two dose levels will be considered (see section 6 for details of this process). If the toxicity is determined to be related to dabrafenib (i.e. palmar-plantar erythrodysesthesia syndrome, arthralgia) then the dose of dabrafenib will be reduced first to 75 mg BID and then increased to 100 mg BID if that first dose level is tolerated. If the toxicity is determined to be related to trametinib, then the dose of trametinib will be reduced to 1 mg QD (if a dose higher than 1 mg QD is being evaluated in the dose cohort) and then increased to 1.5 mg QD if that first dose level is tolerated. Please see section 6.1 for dose modifications of dabrafenib and trametinib. If the toxicity is determined to be related to INCB039110 then the dose will be reduced by 1 dose cohort. At the end of the planned enrollment to the phase 1 portion of the study, a complete review of the PK data and safety will occur before cohort expansion at the MTD.

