5. TREATMENT PLAN

Treatment will be administered on an outpatient basis. A cycle of treatment will be 28 days in length. Patients are asked to maintain a medication diary for recording each dose of Dabrafenib, Trametinib and INCBO39110.

Reported adverse events and potential risks are described in Section 7. Appropriate dose modifications are described in Section 6. No investigational or commercial agents or therapies other than those described below may be administered with the intent to treat the patient's malignancy. The patient will be requested to maintain a medication diary of each dose of medication. The medication diary (Appendix C) and pill bottles will be returned to clinic staff at the end of each course. To document compliance, a pill count will be performed of all unused pills.

Dosing levels for the study are listed below in Table 5.1. Dose level 1 will be the first dose level. Dose escalation to the next dose level will occur when the preceding cohort reaches the end of Cycle 1. Patients who do not complete treatment in cycle 1 for reasons other than dabrafenib, trametinib or INCBO39110 toxicity will be replaced. Intra-patient dose escalation will be allowed when safe and feasible once the next higher dose level has been cleared. Additional, intermediate dose levels may be enrolled under the following conditions:

- 1) Toxicity is seen at a dose level where dose modification is necessary and the prior, lower dose level was treated without DLT or analysis of the PK data suggests that an intermediate dose would be appropriate;
- 2) An intermediate dose is conceivable based on the size of pills and nature of the toxicity at the higher dose;
- 3) IRB approval of an amendment to the protocol that clearly describes the rationale for and the logistics of the intermediate dose level.

Table 5.1 Dose Escalation Levels for Phase I Study

Dose Level	Dabrafenib [BID/PO]	Trametinib [QD/PO]	INCB039110 (mg QD)
-2	75 mg	1 mg	100 mg
-1	150 mg	2 mg	100 mg
1	150 mg	2 mg	200 mg
2	150 mg	2 mg	300 mg
3	150 mg	2 mg	400 mg

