5.3 Definition of Dose Limiting Toxicity

Dose-limiting toxicity (DLT) is based on the CTEP Active Version 4 of the NCI Common Terminology Criteria for Adverse Events (CTCAE). DLT refers to INCB039110, Dabrafenib, or Trametinib treatment-related toxicities experienced during the first cycle of treatment between days 1-28. A DLT will be defined as follows:

- Any grade 4 toxicity
- Grade 3 non-hematologic toxicity
- Grade ≥ 3 neutropenia with fever $> 38.5^{\circ}\text{C}$
- Grade 3 thrombocytopenia with clinically significant bleeding
- Toxicity resulting in patients missing more than 20% of the doses

In general, all Grade 3, non-hematological toxicities related to INCB039110, Dabrafenib, or Trametinib regardless of duration are considered DLT. However, the following Grade 3 toxicities will not be considered a DLT.

- The appearance of cutaneous squamous cell carcinoma or keratoacanthoma will not be considered a dose limiting toxicity as these are commonly observed with dabrafenib.
- Grade 3 fatigue persistent for ≤ 7 days
- Grade 3 nausea, vomiting, or diarrhea persisting ≤ 72 hours with maximum supportive care
- Grade 3 electrolyte events if they are resolved with replacement within 24 hours
- Lymphopenia regardless of grade
- The following grade 3 laboratory abnormalities will not be considered dose limiting if they return to baseline in less than 7 days: elevated bilirubin, AST, ALT, cholesterol, amylase, lipase, creatinine and hypertriglyceridemia

Management and dose modifications associated with the above adverse events are outlined in Section 6.

Patients that have missed more than 20% of the doses for non-toxicity related reasons will not be considered evaluable for DLTs.

Dose escalation will proceed within each cohort according to the following scheme. Dose-limiting toxicity (DLT) is defined above.

Table 5.2. Dose escalation table

Number of Patients with DLT at a Given Dose Level	Dose Escalation Rule
0 out of 3	Proceed to the next dose level and enroll 3 patients
1 out of 3	Enroll and treat 3 additional patients at this dose level.
≥ 2 out of 3	Dose escalation will be stopped. The MTD will be one dose below this dose level. Three (3) additional patients will be entered at the next lower dose level if only 3 patients were treated previously at that dose.
1 out of 6	Proceed to the next dose level.

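### The 3+3 rules do not guarantee a DLT rate below 33% at the MTD, and they leave 0/3 at the highest dose level without a next step or an MTD

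*Combined protocol and SAP*

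**What the plan says.** Section 13.1 (Study Design/Endpoints) describes a standard 3+3 escalation starting at dose level 1 and draws this conclusion from it: "The escalation and stopping rules imply that the incidence rate for DLT will be less than 33% at the MTD".

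The same section defines the target: "The MTD is defined as the highest dose level at which 0 or 1 of six patients has experienced a DLT". The escalation rules appear twice, in Table 5.2 (Section 5.3) and in Section 13.1. After 0 of 3 the instruction is "Proceed to the next dose level and enroll 3 patients". After 1 of 3, three more patients are treated at that level, and 1 of 6 again leads to escalation. After two or more DLTs, escalation stops, the MTD is placed one level lower, and "Three (3) additional patients will be entered at the next lower dose level if only 3 patients were treated previously at that dose".

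The dose tables in Sections 1.2 and 5 end at level 3. Additional levels are foreseen only between existing ones, and Section 5 requires an approved amendment for them.

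Section 13.1 also gives operating characteristics, introduced by "The following table shows the probability of escalating the dose for various true, but unknown, rates of unacceptable toxicity", and plans the interval method: "Toxicity and efficacy rates will be summarized with 90% exact binomial confidence intervals".

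**The concern.** The MTD is the primary endpoint and sets the dose for an expansion cohort of up to 20 patients. Two parts of its specification do not hold together.

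- **The 33% sentence.** It turns a limit on an observed count into a statement about incidence. A reader assessing the safety of the expansion dose would take it as a property of the design. The escalation table in the same section shows that doses with true rates well above 33% can be cleared, and a cleared dose can become the MTD.
- **The highest level.** The row for 0 of 3 cannot be carried out at level 3, and no other row brings that level to six patients. On the most favourable course of the trial, with no DLT at any level, the primary endpoint has no value under the stated definition.

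**Working it through.** **Inputs.** The escalation rules and MTD definition are from Sections 5.3 and 13.1, the dose levels from Table 5.1, and the escalation probabilities and 90% exact interval from Section 13.1. The documents give no assumed DLT rate per level, so the rates in step 4 are assumptions.

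**1. Reproduce the plan's table, then evaluate the MTD criterion.** A dose is cleared by 0/3, or by 1/3 followed by 0/3:

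f(p) = (1−p)³ + 3p(1−p)²·(1−p)³ = (1−p)³ + 3p(1−p)⁵

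The criterion of at most 1 DLT in six treated patients is met with probability

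g(p) = (1−p)⁶ + 6p(1−p)⁵

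| True DLT rate p | Plan's escalation probability | f(p) | g(p) |
|---|---|---|---|
| 0.10 | 0.91 | 0.906 | 0.886 |
| 0.20 | 0.71 | 0.709 | 0.655 |
| 0.30 | 0.49 | 0.494 | 0.420 |
| 1/3 | not given | 0.428 | 0.351 |
| 0.40 | 0.31 | 0.309 | 0.233 |
| 0.50 | 0.17 | 0.172 | 0.109 |
| 0.60 | 0.08 | 0.082 | 0.041 |

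The plan's table is correct. g(p) is conditional on six patients being treated at the dose; it is not the probability that the dose is named MTD.

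**2. What the qualifying results say about the true rate.** Exact (Clopper-Pearson) upper limits:

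- 0/6, two-sided 90%: 1 − 0.05^(1/6) = 0.393. One-sided 90%: 1 − 0.10^(1/6) = 0.319.
- 1/6, two-sided 90%: the p solving g(p) = 0.05, which is 0.582. One-sided 90%: the p solving g(p) = 0.10, which is 0.510.

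After 1/6 the limit is far above 33% on either convention. After 0/6 it is above 33% two-sided and just below it one-sided.

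**3. Trace the rules at level 3.**

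- 0/3: the row says to move up, and there is no level above. The row that adds three patients applies to the level below one that proved too toxic, so it cannot apply to level 3. The level stays at three patients and does not meet the definition.
- 1/3, then 1/6: the row again says to move up, but six patients have been treated and the definition is met.
- Two or more DLTs: the MTD is sought at level 2.

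Read literally, level 3 can therefore qualify only if it has produced a DLT. If levels 1, 2 and 3 are all 0/3, no dose qualifies. If level 1 or 2 was cleared at 1/6 and level 3 is 0/3, the definition names that lower level.

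**4. How often this path is taken, under assumed true rates at levels 1/2/3.**

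All three levels 0/3: (1−p₁)³(1−p₂)³(1−p₃)³. Any path ending 0/3 at level 3: f(p₁)·f(p₂)·(1−p₃)³.

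| Assumed rates | All 0/3 | Any path ending 0/3 at level 3 | Difference (literal MTD is level 1 or 2) |
|---|---|---|---|
| 5/8/10% | 0.95³ × 0.92³ × 0.90³ = 0.487 | 0.9734 × 0.9369 × 0.729 = 0.665 | 0.178 |
| 10/15/20% | 0.90³ × 0.85³ × 0.80³ = 0.229 | 0.9061 × 0.8138 × 0.512 = 0.378 | 0.148 |

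At 25/35/45% the second quantity is 0.040. Differences use unrounded values.

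**The case against.** **The sentence may describe the observed rate.** The stopping threshold is 2 of 6, which is 33%, and the MTD must fall below it. On that reading the sentence follows from the rules, and the table of true rates beside it tells the reader that toxic doses can be cleared. No sample size or analysis depends on the sentence. But the text speaks of an incidence rate that will be below 33%, whereas the largest observed rate the definition allows is 1/6, or 16.7%. Disclosing the clearance probabilities contradicts the claim rather than qualifying it.

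**The interval argument depends on convention.** Section 13.1 does not say whether the toxicity interval is one- or two-sided, and it plans that interval in the paragraph on the expansion cohort. The sidedness point stands for 0/6 only; 1/6 is an allowed MTD result and fails on both conventions. It also stands that applying the interval to six escalation patients extends the plan's wording.

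**The gap may be only a missing line.** Section 13.2 budgets four cohorts of six, so six patients at level 3 may have been intended, and Section 1.2 says that "a complete review of the PK data and safety will occur before cohort expansion at the MTD". Neither is a decision rule. The expansion opens only once the MTD is known, so it cannot supply the missing patients.

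**The frequencies rest on assumed rates.** This stands: nothing in the documents supports 5 to 10% for the triplet, and with high true rates the gap is seldom reached. Its existence does not depend on those rates.

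**Conclusion.** Both parts hold. The 33% sentence states a safety property that the rules do not have: at a true rate of exactly one third, a dose is cleared with probability 0.43, and six patients treated there meet the MTD criterion with probability 0.35. These figures are exact and need no assumption beyond independent patients with a common DLT rate at the dose.

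The gap at level 3 follows from the text alone. How often it matters depends on the unknown true rates: about two thirds of trials at 5/8/10%, 38% at 10/15/20%, and 4% at 25/35/45%.

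The escalation table is right and the design can stand. The claim drawn from it and the rule at the top level should be corrected.

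**What to change.** In Section 13.1, replace the 33% sentence with wording such as: *Declaring an MTD requires an observed 0 or 1 DLT in six patients; this does not bound the true DLT rate. If six patients are treated at a dose whose true rate is 33.3%, 40% or 50%, the criterion is met with probability 0.35, 0.23 or 0.11.* Refer from there to the existing escalation table. State that the planned 90% exact interval will also be given for the DLT rate at the MTD, and whether it is one- or two-sided.

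In Table 5.2 and its copy in Section 13.1, reconcile the 0-of-3 row with the six-patient MTD definition at the highest listed level. Which rule applies there is the sponsor's decision.

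The cost is a few lines of text. The stated safety property becomes less favourable, and any effect on patient numbers depends on the rule chosen for the highest level.

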13.2 Sample Size/Accrual Rate

The total enrollment of this trial will be between 4 and 38 evaluable patients. The minimum would occur if the triple combination proved too toxic at dose levels 1 and -1 and the trial was stopped during the dose escalation phase. A maximum enrollment of 38 patients reflects four complete dose escalation cohorts of 6 patients each and the expansion cohort of 20 total patients at the MTD. Assuming an accrual rate of 2-3 patients per month, we estimate a maximum enrollment period of 20 months.

13.3 Analysis of Secondary, Correlative, and Exploratory Endpoints

The response rate will be presented as a point estimate with a 90% exact binomial confidence interval. The one-year disease-free and overall survival after treatment will be estimated using the product-limit methods of Kaplan-Meier, and presented with 90% confidence intervals. Standard errors will be estimated using log(-log(survival)) methodology.

13.3.1 Correlatives and exploratory endpoints

- Pharmacokinetics

Pharmacokinetic parameters, including maximal plasma or serum concentration (Cmax), area under the curve to the last collection point (AUClast), area under the curve for dose interval (AUC0-t), and time of maximal concentration (Tmax), will be determined.

Descriptive statistics including mean, standard deviation, coefficient of variation, geometric mean, median, minimum and maximum will be computed for each pharmacokinetic variable; descriptive statistics for natural-log transformed pharmacokinetic variables will also be provided.

- **Exploratory Analyses**

Factors related to prior therapy and features of therapy will be collected and explored with respect to efficacy outcomes. These include whether or not participants had prior treatment with any of the following agents – pembrolizumab, nivolumab, ipilimumab, atezolizumab, or high-dose IL-2 – and the time of last dose for each. Subset analyses will be performed to assess for indications of differential outcomes. Additionally, on-study features such as dose reductions or discontinuations (of any or all study drugs) will also be taken into consideration.

- **Evaluation of the RNF125-JAK1-AXL/EGFR axis**

In order to characterize the changes on the tumor and its microenvironment during and following inhibition of the RNF125-JAK1-AXL/EGFR axis, we will use single-cell resolving technologies developed by our collaborators at the Dana-Farber/Harvard Cancer Center and apply them to pre-, on- and post-treatment biopsy specimens. Our collaborators in the [name] and [name] labs at DF/HCC have developed a platform for processing single-cell isolates from patient specimens to generate single-cell transcriptome profiles (sc-RNAseq). (Tirosh *et al.*, 2016) Through a process of disaggregation into single cells, fluorescence-activated flow sorting, RNA isolation and massively paralleled sequencing of complementary DNA libraries, this technology permits the deconvolution of intra-tumoral heterogeneity and enhanced granularity of the tumor ecosystem compared to bulk RNA sequencing. With assistance from our collaborator [name] of the [name]/[name] labs, we will perform single-cell RNA sequencing on pre-, on- and post-treatment patient specimens to evaluate for gene expression profiles that correlate with drug-resistance or predict treatment response. Cell states will be analyzed via: 1) unbiased assessment of the intercellular transcriptional heterogeneity using principal component analysis (PCA) followed by downstream enrichment analysis of emerging principal components (PCs); and 2) Gene Set Enrichment Analysis (GSEA) to specifically assess the activity and variability of hundreds of pathways across cells within the same tumor.

We will also utilize highly multiplexed imaging via a high-throughput cyclic immunofluorescence (CycIF) method developed by the [name] lab at DF/HCC to perform deep-profiling at the protein level of single-cells from patient specimens. (Lin *et al.*, 2015) Our collaborator [name] of DF/HCC has optimized this technique - which can permit up to 30 protein markers per slide - for formalin-fixed paraffin embedded patient-tumor specimens (personal communication of unpublished data). We will leverage this approach to validate that proof of mechanism and target engagement of INC039110 by evaluating RNF125-JAK1-AXL/EGFR axis proteins implicated in therapeutic escape including BRAF, CRAF, AKT, JAK1, phospho-AKT, phospho-ERK, phospho-STAT3, EGFR and AXL. We will also use CycIF to immunophenotype tumor-infiltrated lymphocytes and tumor-associated macrophages to characterize the effects of triple JAK1i/BRAFi/MEKi targeting on the immune cell microenvironment. Multi-spectral CycIF images are segmented using freely available tools (ImageJ, CellProfiler) to generate a coordinate map against which fluorescence intensities for all channels can be aligned. Data from 10^5 - 10^7 cells can then be visualized as images and/or studied using dimensionality reduction methods such as principal component analysis or t-Distributed Stochastic Neighbor Embedding.

Furthermore, biopsy specimens will be evaluated by Reverse Phase Protein Array (RPPA) at RPPA Core Facility, [name] Anderson Cancer Center (Texas, USA). Primary targets of interest for

analysis of INCB039110 effect on relevant RNF125-JAK1-AXL/EGFR axis proteins in tumor biopsy tissue will be evaluated. Frozen biopsy specimens obtained during collection will be sent for analysis of protein expression, protein phosphorylation and effects on relevant signaling pathways. 10-15 mg of tumor tissue should be provided for protein extraction and all tumor tissue must be supplied in Precellys tubes with Precellys beads for homogenization. Evaluation will depend upon availability of validated antibodies at MD Anderson Cancer Center. Equivalent biopsy specimens embedded in OCT will be evaluated for tumor and necrotic content.

Skyline version 1.3 will be used for data evaluation. Peaks will be evaluated by comparison of their elution time and fragment ion signal ratios to their matched internal standards. All transitions above 10% of the base peak were used for quantification. Data will be exported to Excel for calculations of protein quantity, standard deviation, and CV (%).

